3. STUDY DESIGN AND SELECTION OF PATIENTS

While the estimates of *ESR1* mutations in advanced breast cancers have varied across studies, data from SoFEA and PALOMA3 show that *ESR1* mutations were typically associated with sensitivity to prior endocrine therapy and secondary resistance. Secondary or acquired resistance is defined as relapse while on adjuvant endocrine therapy after at least 2 years, or relapse within 12 months of completion of adjuvant endocrine therapy or relapse after 6 months of endocrine therapy for MBC [31]. SoFEA trial enrolled patients with no disease progression or relapse on non-steroidal AI for at least 12 months in the adjuvant setting or at least 6 months in the metastatic setting as first line treatment. In SoFEA trial, nearly 90% of *ESR1* mutations observed in MBC patients who had received AI for at least 12 months. While PALOMA3 study enrolled a more varied population, 93% of *ESR1* mutations were observed in patients who were deemed sensitive to prior endocrine therapy suggesting that *ESR1* mutations are seldom associated with primary resistance [9]. Consequently, to identify *ESR1* mutations, HR positive (ER >10%) MBC patients who are on AI with CDK4/6 inhibitor (palbociclib, ribociclib, or abemaciclib) as first line therapy for at least 12 months would be screened for ctDNA analysis. Patients with *ESR1* alterations in ctDNA would be enrolled and randomized.

It is anticipated that approximately 400 MBC patients who are on AI with CDK4/6 as first line therapy for at least 12 months will be screened for ctDNA analysis in order to identify approximately 124 eligible patients with *ESR1* alterations in ctDNA. For screening, approximately 20 mL of peripheral blood will be collected in Streck™ tubes (see **Table 1**). The results from the screening ctDNA tests will be reported to treating physicians. Patients must meet all inclusion and exclusion criteria prior to treatment. The written informed consent must be obtained from the patient prior to screening. The following criteria apply to all patients enrolled onto the study unless otherwise specified.

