7. MEASUREMENT OF EFFECT

7.1. RECIST Criteria in metastatic disease

Tumor response for patients with measurable lesions should be assessed using RECIST 1.1[32]. Patients with measurable lesions should be assessed using contrast-enhanced CT of the chest, abdomen and/or MRI scan of the chest, abdomen and pelvis approximately (+/- 7 days) every three cycles (cycle length is 28 days), from the date of first dose of fulvestrant until the 30-day follow-up visit. Although progression may be determined by the investigator based upon clinical deterioration, every effort should be made to document progression using radiographic methods. The basis for determination of progression per clinical deterioration should be documented.

Note: It is very important that the same method of radiologic assessment be used throughout the study and that the same lesions are followed.

Response Criteria

Changes in the largest diameter of the tumor lesions and the shortest diameter in the case of malignant lymph nodes should be used in RECIST assessment.

Complete Response (CR): Disappearance of all target lesions. Any pathological lymph nodes (whether target or non-target) must have reduction in short axis to <10 mm.

Partial Response (PR): At least a 30% decrease in the sum of the diameters of target lesions, taking as reference the baseline sum diameters.

Progressive Disease (PD): At least a 20% increase in the sum of the diameters of target lesions, taking as reference the smallest sum on study (this includes the baseline sum if that is the smallest on study). In addition to the relative increase of 20%, the sum must also demonstrate an absolute increase of at least 5 mm. (Note: the appearance of one or more new lesions is also considered progressions).

Stable Disease (SD): Neither sufficient shrinkage to qualify for PR nor sufficient increase to qualify for PD, taking as reference the smallest sum diameters while on study.

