8. BIOMARKER AND CORRELATIVE STUDIES

ctDNA analysis

To identify *ESR1* alterations, patients will have mandatory ctDNA assessment prior to randomization. In addition, to assess mutant allele fraction/ somatic allele burden (SAB) plasma for ctDNA would be obtained at 4, 12 weeks, and at progression. Blood draw for ctDNA would be stored in Guardant360 StreckTM cell preservation tubes (8-10 mL x 2 per blood draw). Where possible, blood samples for ctDNA will be drawn from patients scheduled to have venipuncture for standard of care labs assessments for clinical care. Patients with activating *ESR1* mutations will be treated until radiological disease progression. To characterize candidate mechanisms of resistance, Guardant 360 ctDNA analyses will be performed at disease progression and compared with pre-treatment ctDNA analyses. Specifically, we will evaluate alterations in *TP53* and *PIK3CA* and correlate with PFS. We will also evaluate for acquired *RB* mutations as well as other emergent genomic alterations with exposure to CDK inhibitors. We will correlate ctDNA dynamics with changes in CA 15-3 tumor marker. We will also correlate ctDNA dynamics and velocity with responses seen on imaging.

Solid Tumor Genomic Assay 2018									
Hotspot Genes				Full-Length		Copy Number		Gene Fusions	
n = 87				n = 48		n = 47		n = 51	
AKT1	FGFR1	MAP2K1	RAF1	ARID1A	NOTCH3	AKT1	IGF1R	AKT2	MYBL1
AKT2	FGFR2	MAP2K2	RET	ATM	PALB2	AKT2	KIT	ALK	NF1
AKT3	FGFR3	MAP2K4	RHEB	ATR	PIK3R1	AKT3	KRAS	AR	NOTCH1
ALK	FGFR4	MAPK1	RHOA	ATRX	PMS2	ALK	MDM2	AXL	NOTCH4
AR	FLT3	MAX	ROS1	BAP1	POLE	AR	MDM4	BRAF	NRG1
ARAF	FOXL2	MDM4	SF3B1	BRCA1	PTCH1	AXL	MET	BRCA1	NTRK1
AXL	GATA2	MED12	SMAD4	BRCA2	PTEN	BRAF	MYC	BRCA2	NTRK2
BRAF	GNA11	MET	SMO	CDK12	RAD50	CCND1	MYCL	CDKN2A	NTRK3
BTK	GNAQ	MTOR	SPOP	CDKN1B	RAD51	CCND2	MYCN	EGFR	NUTM1
CBL	GNAS	MYC	SRC	CDKN2A	RAD51B	CCND3	NTRK1	ERBB2	PDGFRA
CCND1	H3F3A	MYCN	STAT3	CDKN2B	RAD51C	CCNE1	NTRK2	ERBB4	PDGFRB
CDK4	HIST1H3B	MYD88	TERT	CHEK1	RAD51D	CDK2	NTRK3	ERG	PIK3CA
CDK6	HNF1A	NFE2L2	TOP1	CREBBP	RB1	CDK4	PDGFRA	ESR1	PPARG
CHEK2	HRAS	NRAS	U2AF1	FANCA	RNF43	CDK6	PDGFRB	ETV1	PRKACA
CSF1R	IDH1	NTRK1	XPO1	FANCD2	SETD2	CDKN2A	PIK3CA	ETV4	PRKACB
CTNNB1	IDH2	NTRK2		FANCI	SLX4	CDKN2B	PIK3CB	ETV5	PTEN
DDR2	JAK1	NTRK3		FBXW7	SMARCA4	EGFR	PPARG	FGFR1	RAD51B
EGFR	JAK2	PDGFR		MLH1	SMARCB1	ERBB2	RICTOR	FGFR2	RAF1
ERBB2	JAK3	PDGFRB		MRE11A	STK11	ESR1	TERT	FGFR3	RB1
ERBB3	KDR	PIK3CA		MSH2	TP53	FGF19	TSC1	FGR	RELA
ERBB4	KIT	PIK3CB		MSH6	TSC1	FGF3	TSC2	FLT3	RET

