9. STATISTICAL CONSIDERATIONS

Primary/Secondary Objectives:

This is a randomized, open-label, Phase II, for HR positive advanced breast cancer patients who have been treated with AI and CDK as first line in the metastatic setting for at least 12 months and who have *ESR1* mutations identified through ctDNA assay.

[name], MS, Department of Biostatistics at MD Anderson Cancer Center, will oversee the implementation of the statistical analysis. The primary endpoint is PFS, which is measured from the date of study randomization to the date of event (ie, death and/or disease progression) or the date of last follow-up if no event has occurred. Survival curves for PFS will be analyzed using the Kaplan-Meier method and survival difference across groups will be examined by log rank test. Patients alive and disease-free at the latest clinical evaluation will be censored for PFS at the date of that evaluation. We will estimate the treatment comparison with 95% confidence intervals and p-value using Cox proportional hazards regression and we will assess the proportional hazard assumption using graphs of rescaled Schoenfeld residuals and related tests. We would attempt to identify independent predictors of PFS using multivariable Cox PH regression analysis. Analysis for OS and PFS from the start of next line of therapy will be performed as described for PFS from the date of randomization. Randomization will be performed using Core. Stratification factors include recurrence free interval (\leq 3 years vs. $>$ 3 years), prior adjuvant endocrine therapy (tamoxifen vs. aromatase inhibitor), and site of metastasis (bone vs. visceral).

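### PFS can count progression called on clinical deterioration by an unblinded investigator, with no criteria and no planned analysis that separates such calls from radiographic events

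*Combined protocol and SAP*

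**What the plan says.** - **Endpoint (Section 9).** "The primary endpoint is PFS, which is measured from the date of study randomization to the date of event (ie, death and/or disease progression". No criterion, assessor or dating rule for progression is attached.
- **Clinical route (Section 7.1).** "Although progression may be determined by the investigator based upon clinical deterioration", "every effort should be made to document progression using radiographic methods". The section adds: "The basis for determination of progression per clinical deterioration should be documented". It gives no criteria for what counts as deterioration.
- **RECIST scope (Sections 7.1, 3.1, 9).** RECIST 1.1 is specified for patients with measurable lesions. Measurable disease is not an inclusion criterion, and bone versus visceral metastasis is a stratification factor.
- **Blinding (Sections 9 and 3).** "This is a randomized, open-label, Phase II" trial. "The results from the screening ctDNA tests will be reported to treating physicians".
- **Where scans are done (Section 5.1, Appendix 1).** Staging scans are to be done at the sponsor's centre even when treatment is given locally. No blinded reading is described.
- **Stopping treatment.** Section 5.5 ends protocol therapy at progression as defined in Section 7. Section 8 says patients with activating ESR1 mutations "will be treated until radiological disease progression".
- **Planned analyses (Section 9).** Kaplan-Meier, log-rank and Cox analyses of PFS. None distinguishes how progression was established.

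**The concern.** Section 7 is the only place where progression is defined, so Section 9 read with Section 7.1 lets a clinical call become a primary-endpoint event. The person making that call knows the arm. Treating physicians also know that the patient carries a mutation that the rationale (Section 1.6) links to AI resistance. A physician who takes that view could act sooner on ambiguous symptoms in a patient left on AI than in one moved to fulvestrant.

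Earlier calls in the AI arm alone would shorten control PFS with no drug effect behind it and move the comparison towards fulvestrant. No analysis in the plan would show whether this had happened, although the information needed is to be recorded anyway.

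**Working it through.** **1. The plan's own figures.** Inputs from Section 9: medians 5 and 9 months, two-sided 5% alpha, 80% power, 124 patients, 4-5 patients per month, 5 months of follow-up. 1:1 allocation is assumed, because the ratio is not stated.

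- HR = 5/9 = 0.556 (exponential PFS).
- Freedman events = (1.960 + 0.842)² × [(1 + HR)/(1 − HR)]² = 7.85 × 12.25 ≈ 96.2, so 97.
- Expected events per arm = n[1 − e^(−λf)(1 − e^(−λA))/(λA)], with λ = ln 2/median, f = 5 and A = 124/rate. The sample size for 97 events is 121, 123 or 125 at 4, 4.5 or 5 patients per month, against 124 stated.
- At 124 patients and 5 per month, 53.3 + 43.2 = 96.5 events are expected. Fixed-design power is 82.3%.
- With the stated interim rules (final critical value 1.96 assumed), power is 80.7% with 84.8 events on average, against 81% and 84 stated.

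The design figures reproduce if 84 is read as an average that allows for early stopping. They neither support nor weaken this point, which concerns what counts as an event.

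**2. Can a clinical call be a PFS event?** Section 9 says disease progression and gives no definition. Section 5.5 sends the reader to Section 7 for progression. Section 7.1 allows a clinical determination. So it can, by reading the sections together; Section 7.1 does not itself mention PFS.

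**3. How much could unequal calling matter?** The documents give no rate of clinical-only calls, so the following is illustrative.

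*Model:* no true effect (same exponential median in both arms), 62 patients per arm, uniform accrual over 124/4.5 = 27.6 months plus 5 months of follow-up, log-rank test at 1.96, no interim look. A share of control-arm events is brought forward; none is in the fulvestrant arm. The 3-month shift is about one Section 7.1 scan interval (3 × 28 = 84 days, or 84/30.44 = 2.76 months). The 1.5-month shift is about half of it, the average lead if calls fall evenly between scans.

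Results with 20% of control events early, medians 5 to 9 months:

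| Shift | False wins for fulvestrant (nominal 2.5%) | Two-sided error (nominal 5%) |
|---|---|---|
| 1.5 months | about 3.4-4.2% | about 5.4-5.9% |
| 3 months | about 5.0-5.9% | about 6.4-7.1% |

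At medians of 7 and 9 months the spurious HR is about 0.96-0.97 (1.5 months) or 0.93-0.94 (3 months). At the same medians with a 3-month shift, false wins are 3.1-4.0% for a 10% share and 5.8-7.3% for a 30% share. The planned control median of 5 months is the most sensitive: at a 20% share and 3 months, repeat runs gave 6.0% and 6.8%, so the upper end of the table is approximate.

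**4. Check with scan-based detection.** Median 5 months in both arms, progression detected only at 84-day scans, early calls half an interval (1.38 months) before the detecting scan, 20,000 trials per row:

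| Share called early | False wins for fulvestrant | Two-sided error |
|---|---|---|
| 0% | 2.7% | 5.3% |
| 10%, control only | 4.0% | 5.7% |
| 20%, control only | 5.8% | 6.7% |
| 30%, control only | 8.0% | 8.7% |
| 50%, control only | 13.0% | 13.2% |
| 30%, both arms | 2.7% | 5.1% |

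The simulation standard error at 5% is √(0.05 × 0.95/20,000) ≈ 0.15 percentage points. The last row shows that clinical calling does no harm in itself. The inflation comes from a difference between arms.

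**The case against.** The strongest case against is that there is one definition, not two. Sections 5.5 and 9 both lead naturally to Section 7, which discourages clinical-only calls by asking for radiographic documentation and a written basis. Scans are done at one centre. The protocol states that the best therapy for ESR1-mutant disease is unknown, so investigators need not favour either arm. Patients enter with ECOG 0-1 and without clinical progression.

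Much of this stands, and it rules out three stronger readings that a reader might infer.

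- *That Section 8 sets a rival definition of the primary endpoint.* It does not. Its sentence, "mutations will be treated until radiological disease progression", is about how long treatment continues. It conflicts with Sections 5.5 and 7.1 on stopping treatment. The endpoint fault is Section 9's silence.
- *That control patients will be called early.* The documents show the opportunity and a possible motive, but no rate of clinical calls in either arm. Only *could* is supported.
- *That clinical calls are unrestrained.* Section 7.1 does restrain them. But its measures are an effort clause and a record. Neither keeps a clinical-only call out of PFS, and no analysis uses the record. Scans at one centre do not help where the call needs no scan.

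Counting clinical progression is not wrong in itself, since ignoring real deterioration has its own bias.

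**Conclusion.** The point holds as an unspecified event definition in an unblinded trial, with no analysis able to show whether clinical calls differed by arm. It does not show that the result will be biased.

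If 20% of control events only are called early, false wins for fulvestrant rise from 2.5% to about 3.4-4.2% (1.5 months) or 5.0-5.9% (3 months), and two-sided error from 5% to about 5.4-5.9% or 6.4-7.1%. This rests on an assumed share and lead time, 1:1 allocation, exponential PFS, medians of 5 to 9 months and no interim look. With equal calling in both arms the inflation disappears. The plan should be changed, because the effect is moderate, cannot be checked as the plan stands, and is cheap to make visible.

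**What to change.** 1. State in Section 9 that progression for PFS is as defined in Section 7, and how a clinical call is dated.
2. Pre-specify a sensitivity analysis that counts only radiographic progression or death: RECIST 1.1 for measurable disease, and new lesions or unequivocal progression on imaging for non-measurable or bone-only disease. Without the second part the analysis could not be applied to every patient.
3. Tabulate clinical-only calls by arm, using the basis that Section 7.1 already requires to be documented.
4. Separately, the sponsor must reconcile Section 8 with Sections 5.5 and 7.1 on when treatment stops. Which rule is right is not a statistical question.

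Cost: wording, one extra analysis and one table. Sample size, alpha and visits do not change. Downside: censoring clinical-only calls in the sensitivity analysis may be informative, because those patients may be deteriorating. Report both analyses side by side.

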8. BIOMARKER AND CORRELATIVE STUDIES

ctDNA analysis

To identify *ESR1* alterations, patients will have mandatory ctDNA assessment prior to randomization. In addition, to assess mutant allele fraction/ somatic allele burden (SAB) plasma for ctDNA would be obtained at 4, 12 weeks, and at progression. Blood draw for ctDNA would be stored in Guardant360 StreckTM cell preservation tubes (8-10 mL x 2 per blood draw). Where possible, blood samples for ctDNA will be drawn from patients scheduled to have venipuncture for standard of care labs assessments for clinical care. Patients with activating *ESR1* mutations will be treated until radiological disease progression. To characterize candidate mechanisms of resistance, Guardant 360 ctDNA analyses will be performed at disease progression and compared with pre-treatment ctDNA analyses. Specifically, we will evaluate alterations in *TP53* and *PIK3CA* and correlate with PFS. We will also evaluate for acquired *RB* mutations as well as other emergent genomic alterations with exposure to CDK inhibitors. We will correlate ctDNA dynamics with changes in CA 15-3 tumor marker. We will also correlate ctDNA dynamics and velocity with responses seen on imaging.

Solid Tumor Genomic Assay 2018									
Hotspot Genes				Full-Length		Copy Number		Gene Fusions	
n = 87				n = 48		n = 47		n = 51	
AKT1	FGFR1	MAP2K1	RAF1	ARID1A	NOTCH3	AKT1	IGF1R	AKT2	MYBL1
AKT2	FGFR2	MAP2K2	RET	ATM	PALB2	AKT2	KIT	ALK	NF1
AKT3	FGFR3	MAP2K4	RHEB	ATR	PIK3R1	AKT3	KRAS	AR	NOTCH1
ALK	FGFR4	MAPK1	RHOA	ATRX	PMS2	ALK	MDM2	AXL	NOTCH4
AR	FLT3	MAX	ROS1	BAP1	POLE	AR	MDM4	BRAF	NRG1
ARAF	FOXL2	MDM4	SF3B1	BRCA1	PTCH1	AXL	MET	BRCA1	NTRK1
AXL	GATA2	MED12	SMAD4	BRCA2	PTEN	BRAF	MYC	BRCA2	NTRK2
BRAF	GNA11	MET	SMO	CDK12	RAD50	CCND1	MYCL	CDKN2A	NTRK3
BTK	GNAQ	MTOR	SPOP	CDKN1B	RAD51	CCND2	MYCN	EGFR	NUTM1
CBL	GNAS	MYC	SRC	CDKN2A	RAD51B	CCND3	NTRK1	ERBB2	PDGFRA
CCND1	H3F3A	MYCN	STAT3	CDKN2B	RAD51C	CCNE1	NTRK2	ERBB4	PDGFRB
CDK4	HIST1H3B	MYD88	TERT	CHEK1	RAD51D	CDK2	NTRK3	ERG	PIK3CA
CDK6	HNF1A	NFE2L2	TOP1	CREBBP	RB1	CDK4	PDGFRA	ESR1	PPARG
CHEK2	HRAS	NRAS	U2AF1	FANCA	RNF43	CDK6	PDGFRB	ETV1	PRKACA
CSF1R	IDH1	NTRK1	XPO1	FANCD2	SETD2	CDKN2A	PIK3CA	ETV4	PRKACB
CTNNB1	IDH2	NTRK2		FANCI	SLX4	CDKN2B	PIK3CB	ETV5	PTEN
DDR2	JAK1	NTRK3		FBXW7	SMARCA4	EGFR	PPARG	FGFR1	RAD51B
EGFR	JAK2	PDGFR		MLH1	SMARCB1	ERBB2	RICTOR	FGFR2	RAF1
ERBB2	JAK3	PDGFRB		MRE11A	STK11	ESR1	TERT	FGFR3	RB1
ERBB3	KDR	PIK3CA		MSH2	TP53	FGF19	TSC1	FGR	RELA
ERBB4	KIT	PIK3CB		MSH6	TSC1	FGF3	TSC2	FLT3	RET
ERCC2	KNSTRN	PPP2R1A		NBN	TSC2	FGFR1		JAK2	ROS1
ESR1	KRAS	PTPN11		NF1		FGFR2		KRAS	RSPO2
EZH2	MAGOH	RAC1		NF2		FGFR3		MDM4	RSPO3
				NOTCH1		FGFR4		MET	TERT
				NOTCH2		FLT3		MYB	

For patients with tumor sites amenable to biopsy, repeat tumor biopsies at the time of disease progression may be performed as standard of care and subjected to tumor genomic analysis by next generation sequencing (NGS). Tumor genomic analysis would be performed using Oncomine Solid Tumor Genomics Assay 2018 (STGA2018, V3) in the Molecular Diagnostics Laboratory at MDACC. Tissue based tumor genome sequencing is approved in standard care for patients with metastatic breast cancers at MDACC by the Molecular Testing Evaluation Committee (MTEC). Genomic alterations identified by tissue based

Proprietary of MD Anderson Cancer Center

Protocol 2018-0287

January 8, 2020

NGS will be correlated with genomic alterations identified by ctDNA analysis. Genomic alterations assessed by STGA2018 are listed above.

9. STATISTICAL CONSIDERATIONS

Primary/Secondary Objectives:

This is a randomized, open-label, Phase II, for HR positive advanced breast cancer patients who have been treated with AI and CDK as first line in the metastatic setting for at least 12 months and who have *ESR1* mutations identified through ctDNA assay.

[name], MS, Department of Biostatistics at MD Anderson Cancer Center, will oversee the implementation of the statistical analysis. The primary endpoint is PFS, which is measured from the date of study randomization to the date of event (ie, death and/or disease progression) or the date of last follow-up if no event has occurred. Survival curves for PFS will be analyzed using the Kaplan-Meier method and survival difference across groups will be examined by log rank test. Patients alive and disease-free at the latest clinical evaluation will be censored for PFS at the date of that evaluation. We will estimate the treatment comparison with 95% confidence intervals and p-value using Cox proportional hazards regression and we will assess the proportional hazard assumption using graphs of rescaled Schoenfeld residuals and related tests. We would attempt to identify independent predictors of PFS using multivariable Cox PH regression analysis. Analysis for OS and PFS from the start of next line of therapy will be performed as described for PFS from the date of randomization. Randomization will be performed using Core. Stratification factors include recurrence free interval (\leq 3 years vs. $>$ 3 years), prior adjuvant endocrine therapy (tamoxifen vs. aromatase inhibitor), and site of metastasis (bone vs. visceral).

To detect a change in median PFS from 5 months (for AI arm) to 9 months (with fulvestrant arm) would require about 124 patients (assuming 4-5 patients per month accrual, 5 months post-accrual follow-up, 5% two-sided alpha, 80% power, log rank testing). 84 PFS events are expected under the alternative hypothesis. Interim analysis will be performed when 42 PFS events are observed. Using O'Brien-Fleming stopping boundaries, we will stop for futility if the log rank test p-value $>$ 0.72 and stop for success if it is $<$ 0.004. Descriptive statistics and graphical analysis will be used to summarize patients' demographic and clinico-pathological characteristics, and efficacy outcomes. We will use mean (standard deviation) or median (range) to summarize continuous variables and frequency (percentages) for categorical variables. Graphical analysis, such as scatter plots with Lowess smoothers, will be used to assess the correlative structure of outcomes and compare MAF between fulvestrant and AI treated groups. The Pearson correlation, or its non-parametric analogue, the Spearman correlation, will be used to estimate the linear correlation among variables. Radiographic response rate (partial response + complete clinical response) will be estimated and reported with a 95% CI.

Control	Experimental	
Median	Median	Power
5	6	15%
5	7	38%
5	8	63%
5	9	81%
5	10	91%
5	11	96%
5	12	98%

REFERENCES:

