5. TREATMENT PLAN

5.1. Treatment

- **Fulvestrant** 500 mg should be administered intramuscularly (+/- 3 days) into the buttocks slowly (1 - 2 minutes per injection) as two 5 mL injections, one in each buttock, on days 1, 15 of Cycle 1 and then Day 1 of Cycles 2 and beyond (Cycle = 28 days).
- **Ribociclib** tablets should be taken orally in combination with NSAI (non-steroidal aromatase inhibitor) or fulvestrant. Starting dose – 600 mg orally taken once daily for 21 consecutive days followed by 7 days off treatment.
- **Palbociclib** capsules should be taken orally with food in combination with an NSAI or fulvestrant. Starting dose – 125 mg orally taken once daily for 21 consecutive days followed by 7 days off treatment.
- **Abemaciclib** tablets should be taken orally in combination with NSAI or fulvestrant. Starting dose – 150 mg twice daily
- **Letrozole** 2.5 mg or **anastrozole** 1 mg orally should be taken orally daily
- Pre/Peri-menopausal women treated with CDKI plus NSAI or fulvestrant therapy should be treated with luteinizing hormone-releasing hormone (LHRH) agonists according to current clinical practice standards.

Since treatment involves standard of care agents, patients can pursue treatment outside of MD Anderson, under the supervision of the local oncologist. However, clinical documents to confirm administration should be sent for review. Additionally, clinical assessments to confirm response (e.g. staging scans) should be performed at MD Anderson.

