6.2. Evaluation during study

Follow up laboratory assessments should be performed as per standard of care for palbociclib, ribociclib, abemaciclib, and fulvestrant

- Physical examination (including vital signs, weight, performance status)
- Patients will undergo restaging with complete imaging (CT CAP and bone scan) approximately every 3-4 cycles of therapy for the first 12 months and every 3-6 months thereafter until progression.
- Exploratory ctDNA blood draws (Guardant360 StreckTM cell preservation tubes (8-10 mL x 2 per blood draw) will be performed at Cycle 2, Cycle 4 and Cycle 12. These will be banked at MDACC. ctDNA will be drawn on the same date as standard of care labs assessments.
- End of Treatment/Progression ctDNA Blood draw (Guardant360 StreckTM cell preservation tubes (8-10 mL x 2 per blood draw).

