Appendix 1 Schedule of clinical assessments

Evaluation	Screening	Cycle 1	Cycle 2	Cycle 4	Cycle 12	End of treatment/ Progression
Physical exam, Vital Signs	X ^a					
ECOG PS	X ^a					
Hematology and Chemistry	Z					
Coagulation (PT/PTT/INR)	Z					
Pregnancy Test (urine)*	X					
Liquid Biopsy **	X**		X***	X***	X***	X**
Concomitant medications	X ^a					
Fulvestrant^d administration		X	X	X	X	
Imaging	X ^b			X	X	X
Tumor marker	X		X	X ^c	X	

* For women of child bearing age. Repeated at the discretion of treating physician

^zLabs and clinical monitoring should be performed as per standard of care for CDK4/6 with AI/fulvestrant use

^{**} Guardant ctDNA assessments are collected at screening (for baseline *ESR1* assessment), at progression.

^{***}Exploratory samples for ctDNA assessment will be collected at Cycle 2, Cycle 4 and Cycle 12 and will be banked at MDACC and processed at Guardant Health at the time of study conclusion.

^a All medications (other than study drug) taken within 28 days of starting study treatment through the 30-day safety follow up visit should be reported on the CRF.

^b Tumor imaging (CT/Bone scan) will be performed approximately every 3-4 cycles of therapy for the first 12 months and every 3-6 months thereafter until progression. Tumor imaging should be performed at MD Anderson.

^c Tumor markers (CA 15-3) performed approximately every 3 cycles (12 weeks) until disease progression in coordination with routine labs and imaging

^d Fulvestrant administration for patients randomized to the fulvestrant arm only (+/- 7 days). Second dose of fulvestrant to be administered at C1D15. Control patients would continue the treatment they were already on (CDK inhibitor in combination with aromatase inhibitors). Fulvestrant can be administered under the supervision of treating physician locally.

Proprietary of MD Anderson Cancer Center

Protocol 2018-0287

January 8, 2020

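### With scans 12 to 16 weeks apart and only right-censored methods planned, PFS medians follow the scan grid, and the log-rank and Cox results can be biased if scan timing differs by arm

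*Combined protocol and SAP*

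**What the plan says.** **Analysis.** Section 9 measures PFS from randomization to death or progression. The method is: "Survival curves for PFS will be analyzed using the Kaplan-Meier method and survival difference across groups will be examined by log rank test". Cox regression supplies the treatment comparison with its 95% interval. Section 9 does not say which date counts as the progression date, has no rule for late or missed scans, and plans no interval-censored or schedule-sensitivity analysis.

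**Design.** The sample size is set "To detect a change in median PFS from 5 months (for AI arm) to 9 months (with fulvestrant arm"), "assuming 4-5 patients per month accrual, 5 months post-accrual follow-up, 5% two-sided alpha, 80% power, log rank testing". The trial is open-label and PFS is its only primary endpoint.

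**Imaging.** Three places set the scan schedule:
- Section 6.2 has restaging "approximately every 3-4 cycles of therapy for the first 12 months and every 3-6 months thereafter until progression".
- Appendix 1, footnote b, agrees: "Tumor imaging (CT/Bone scan) will be performed approximately every 3-4 cycles of therapy for the first 12 months".
- Section 7.1, for patients with measurable lesions, has imaging "approximately (+/- 7 days) every three cycles (cycle length is 28 days"), counted "from the date of first dose of fulvestrant until the 30-day follow-up visit".

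Section 7.1 also lets the investigator determine progression from clinical deterioration, while asking for radiographic documentation wherever possible.

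**The concern.** A progression found on imaging is known only to lie between the last progression-free scan and the scan that shows it. Kaplan-Meier, log-rank and Cox take the recorded date as exact. That does little harm when scans are frequent relative to the median. Here one interval can span more than half of the assumed control median.

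Two things are at stake. The recorded medians may mostly show where the scans fall, in a trial whose target is stated in medians. And if one arm tends to be scanned later than the other, its progressions are recorded later and the treatment comparison absorbs the difference. As planned, no analysis would reveal or correct this.

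**Working it through.** **Inputs.** A cycle is 28 days (Section 5.1: "Day 1 of Cycles 2 and beyond (Cycle = 28 days")). Scan intervals are from Sections 6.2 and 7.1 and Appendix 1. The medians (5 and 9 months), 124 patients, 4-5 per month, 5 months of follow-up and 5% two-sided alpha are from Section 9. Assumed here, because the documents do not say: 1:1 allocation, exponential PFS, accrual at 4.5 per month, no dropout.

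**1. The plan's own power.**
- Accrual lasts A = 124/4.5 = 27.6 months, with F = 5.
- P(event) = 1 − [exp(−λF) − exp(−λ(A+F))]/(λA), with λ = ln 2/median. This gives 0.872 for 5 months and 0.718 for 9.
- Expected events = 62 × (0.872 + 0.718) = 98.6.
- With HR = 5/9 = 0.556, Freedman power = Φ(√98.6 × 0.444/1.556 − 1.96) = Φ(0.88) = 81%, as in the Section 9 table.
- The other rows reproduce within two points. The stated 84 events do not follow from these inputs; that is a separate matter and does not affect this point.

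**2. Scan interval against the median.** 12 weeks = 84/30.44 = 2.76 months, and 16 weeks = 112/30.44 = 3.68 months. Divided by 5 months, these are 55% and 74%.

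**3. Recorded medians on a fixed grid.** The latent median is carried to the next scan.

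| Latent median | 12-week grid | 16-week grid |
|---|---|---|
| 5 months (21.7 weeks) | week 24 = 5.5 months | week 32 = 7.4 months |
| 9 months (39.1 weeks) | week 48 = 11.0 months | week 48 = 11.0 months |

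The apparent gain is 11.0 − 5.5 = 5.5 months or 11.0 − 7.4 = 3.7 months (7.36 and 11.04 before rounding), against a latent 4. If intervals vary between 12 and 16 weeks, simulation puts the control median at about 6.7 months.

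**4. Why a small shift matters.** Take no true effect (both medians 5 months), controls scanned at week 12 and fulvestrant patients at week 13, with no censoring.
- Week 12: 62 × (1 − 2^(−12/21.74)) = 19.7 control events. Both arms have 62 at risk, so the log-rank expects 9.85 of these in the fulvestrant arm and sees none.
- Week 13: 62 × (1 − 2^(−13/21.74)) = 21.0 fulvestrant events. At risk are 62 and 42.3, so 21.04 × 62/104.3 = 12.5 are expected.
- Observed minus expected for fulvestrant = 21.0 − 9.85 − 12.5 = −1.3 events from one scan round, with no drug effect. On a common date this is zero.

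**5. Simulated log-rank results.** 124 patients, 1,500 to 4,000 trials per setting, progression found only by scan, no interim look. Fixed intervals carry ±1 week of jitter.

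| Scan intervals (weeks) | No true effect: two-sided error | HR |
|---|---|---|
| Both 12 | 5.0% | 1.00 |
| Both 16 | 4.8% | 1.00 |
| 12-16, unrelated to arm | 5.4% | 1.00 |
| Control 12, fulvestrant 13 | 10.6% | 0.88 |
| Control 12, fulvestrant 14 | 10.6% | 0.89 |
| Control 12, fulvestrant 16 | 8.0% | 0.91 |
| Control 12-14, fulvestrant 14-16 | 11.7% | 0.87 |
| Control 14-16, fulvestrant 12-14 | 10.8% | 1.14 |

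In the 11.7% row, 11.1% are false wins for fulvestrant, against a nominal 2.5%. With true medians of 5 and 9 months, power is 79-81% under a common or arm-unrelated schedule, 88% with control 12 and fulvestrant 16, and 70% with control 16 and fulvestrant 12.

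**6. Dilution.** In a separate run with 30% of progressions dated clinically, the inflated error came down to about 7%.

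**7. Interval-censored analysis.** Under the same data model, a likelihood-ratio test gave error of 5.3% (12/12), 4.5% (12/13) and 5.8% (12/16), with HR 1.00-1.01. Power was 82% (12/12) and 81% (12/16), with HR 0.55. Simulation error is about 0.6 points on the error rates.

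**The case against.** Section 6.2 and Appendix 1 give both arms the same range, and Section 5.1 and Appendix 1 have staging scans done at one institution. Kaplan-Meier, log-rank and Cox on recorded dates are a defensible primary analysis. All of this stands. A single imaging site fixes where scans happen, however, not when.

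A reader might infer that the permitted range in itself produces a false treatment effect. The documents do not support that: nothing assigns the arms different intervals, and variation unrelated to arm left HR at 1.00 and error at 5.4%. Bias needs timing that differs by arm.

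A reader might also infer that the medians will be overstated against the design. That cannot be shown. Section 9 does not say whether its 5 and 9 months are latent or scan-dated; if scan-dated, the recorded medians match the design's own scale.

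A third tempting inference is that controls, already treated for at least 12 months at entry, go straight to the later 3-6 month schedule. The wording does not quite exclude this, but the cycle columns in Appendix 1, with imaging at Cycles 4 and 12, point to on-study time for everyone.

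Two further objections limit the remedy. The interval-censored results come from models that were correct for exponential data, so they are a favourable case. And a non-parametric (Turnbull) median still follows the grid at 62 per arm: in simulation it was typically only an interval, 2.8-5.5 months on 12-week scans or 3.7-7.4 on 16-week scans.

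**Conclusion.** The concern holds in conditional form. It is certain that the permitted interval is 55-74% of the assumed control median, that scan-dated medians sit above latent ones, and that Section 9 contains nothing to detect or adjust for scan timing.

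Bias in the treatment comparison is a risk, not a consequence of the plan. It has a route in the text: treatment is known, Section 7.1 (every three cycles, ±7 days) conflicts with Section 6.2 and Appendix 1 (every 3-4 cycles) for patients with measurable disease, and Section 7.1 gives controls no starting point for the scan clock, while PFS runs from randomization.

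If timing does differ by arm, error with no true effect is about 8-12%. HR is about 0.87-0.91 when fulvestrant patients are scanned later, and above 1 when controls are. These sizes rest on exponential PFS, 1:1 allocation and progression found only by scan; deaths and progression dated by clinical deterioration would reduce them.

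**What to change.** 1. **Section 9.** Keep the log-rank as the primary test. Pre-specify an interval-censored proportional hazards sensitivity analysis, with its HR and 95% CI beside the Cox HR. Enter each imaging progression as the interval from the last progression-free scan to the first scan showing progression. Enter deaths and documented clinical-deterioration progressions as exact dates. Beside the Kaplan-Meier medians, report model-based interval-censored medians, or Turnbull estimates shown as intervals.
2. **Reporting.** Tabulate actual scan intervals by arm, so that a reader can see whether timing differed.
3. **Imaging text.** Reconcile Section 6.2, Section 7.1 and Appendix 1 so that both arms follow the same scan calendar counted from randomization. Which interval to use is for the sponsor to settle.

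Item 3 matters because the log-rank stays the decision test: the sensitivity analysis exposes arm-related timing but does not correct the log-rank's error rate. The cost is a few lines of text and one extra model with a baseline-hazard assumption. The scan dates should already be on record. Reported medians may come out lower than the Kaplan-Meier ones.
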